In addition, any subject presenting with an AE of pelvic / lower abdominal pain and any subject presenting with symptoms she believes are due to hypersensitivity or allergic reaction will be evaluated per standard medical practice. In addition, this evaluation will include collection and submission of blood and serum samples to a central laboratory for a NiLPT, which is a measure of sensitization to nickel; a chromium LPT, which is a measure of sensitization to chromium; serum or plasma nickel level; and serum or plasma titanium level. If removal of a device or any other surgery is performed, pathological evaluation and metallurgic studies (if applicable) will be included. After the evaluation of the subject is complete, regardless of investigator's assessment as to whether or not a hypersensitivity / allergic reaction has occurred, all information will be forwarded to the adjudication committee (see Section 14.3) in a blinded fashion. If pathology / metallurgic studies are provided to the adjudication committee, it may not be possible to blind the members as to which group the subject belongs. Information forwarded to the adjudication committee will include all laboratory work for the subject, including baseline, 12 month (if applicable), and unscheduled draws. The final determination of whether or not a hypersensitivity / allergic event has occurred will be made by this committee.

- **Autoimmune disorders:** The proportion of subjects with adjudicated newly diagnosed or worsening autoimmune disorders in subjects wearing Essure inserts and in subjects undergoing laparoscopic tubal sterilization. Any subject presenting with symptoms indicating a potential autoimmune disorder will be evaluated per standard medical practice. All efforts will be made to obtain records of any diagnostic workup conducted by outside physicians. Blood samples for NiLPT, chromium LPT, serum or plasma nickel level, and serum or plasma titanium level will also be collected by the study site. An appropriate human leukocyte antigen (HLA) panel will be run on previously obtained baseline samples, if not already obtained at baseline. (The specific HLA type to be run will be dependent on the specific autoimmune disease the subject developed). If insufficient baseline sample exists, an additional sample may need to be drawn. After the evaluation of the subject is complete, regardless of investigator's assessment as to whether or not an autoimmune disorder exists, all

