information will be forwarded to the adjudication committee in a blinded fashion. If pathology / metallurgic studies are provided to the adjudication committee, it may not be possible to blind the members as to which group the subject belongs. Information forwarded to the adjudication committee will include all laboratory work for the subject, including baseline, 12 month (if applicable), and unscheduled draws. The final determination of whether or not an autoimmune disorder has occurred will be made by this committee.

- **Proportion of subjects undergoing invasive gynecologic surgery after Essure placement:** (excluding second placement attempts); including Essure insert removal compared to the proportion of subjects undergoing invasive gynecologic surgery after laparoscopic tubal sterilization.
- **Patient reported outcome measures** (details for PROs can be found in Section 9.2.3):
 - Medical Outcomes Study (MOS) Short Form-36 (SF-36; Version 2) (a global measure of quality of life);
 - Screening question for lower abdominal / pelvic pain;
 - PROMIS Scale V1.0 – Pain Intensity 3a - to be completed if screening question is positive (a measure of pain intensity);
 - PROMIS Scale V1.0 – Pain Interference 8a Participant Format - to be completed if screening question is positive (a measure of how pain interferes with daily life);
 - AMSS (includes items querying menstrual volume, regularity, and interference across the previous 3 menstrual periods);
 - Two intermenstrual bleeding questions (probe for instances of vaginal bleeding between periods);
 - Fibromyalgia Survey Questionnaire (FSQ) – for baseline only (a measure of a centralized pain state, shown to be useful in prediction of chronic pain);
 - Supplemental PRO Questionnaires – for use at 12, 24, 36, 48, and 60 months only: a series of PRO tools used to actively solicit information on AEs commonly found in medical device reporting (MDR) reports with Essure;
 - Social Media Questionnaire – for use at 60 months (or Premature Discontinuation visit if applicable) only: to elicit information about sources of influence on medical decisions, in particular, use of social media.

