For potential allergic / hypersensitivity reactions, investigators will be instructed that an evaluation should be performed in any subject presenting with urticaria, angioedema, unexplained rash, unexplained itching, flushing, or anaphylaxis. Evaluation will also be performed in subjects who present with other symptoms that could possibly be related to an inflammatory reaction (e.g., hair loss, fatigue, muscle pain, joint pain, joint swelling). This evaluation will include a NiLPT, which is a measure of sensitized T-cell reactivity to nickel in culture; a chromium LPT, which is a measure of sensitization to chromium; serum or plasma nickel level; and serum or plasma titanium level and an inflammatory cytokines panel. For NiLPT and chromium LPT, both the continuous score as well as the positive / negative score (based on established cut-offs for negative responses) will be recorded. The results of these lab tests will be forwarded to the sponsor directly by the central lab and will be made available to the adjudication committee. In addition, any subject presenting with an AE of pelvic / lower abdominal pain and any subject presenting with symptoms she believes are due to a hypersensitivity or allergic reaction will also be evaluated, including a NiLPT, chromium LPT, serum or plasma nickel level, and serum or plasma titanium level and an inflammatory cytokines panel. If removal of a device or any other surgery is performed, pathological evaluation and metallurgic studies (if applicable) will be included. After the evaluation of the subject is complete, regardless of investigator's assessment as to whether or not a hypersensitivity / allergic reaction has occurred, all information will be forwarded to the adjudication committee in a blinded fashion. In cases of pathological evidence, blinding may not be possible. Final determination of whether or not a hypersensitivity / allergic event has occurred will be based on the determination of this committee. Once adjudicated events are available, the following comparisons will be possible:

- Pathological findings (if sufficient specimens are obtained) in subjects with Essure and adjudicated hypersensitivity reactions can be compared to pathological findings in subjects with Essure without hypersensitivity reactions as well as to pathological findings in laparoscopic tubal ligation subjects (with and without adjudicated hypersensitivity reactions).

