- Levels of inflammatory markers and HLA type in subjects with Essure and adjudicated hypersensitivity reactions can be compared to corresponding findings in subjects with Essure without hypersensitivity reactions as well as to laboratory results in laparoscopic tubal ligation subjects (with and without adjudicated hypersensitivity reactions). Serum cytokine values will be classified as below the normal range, within the normal range, or above the normal range, as appropriate. These values will be used to provide descriptive summaries of change of categories between baseline and

Year 1 and between baseline and Year 5. For these analyses the safety population will be used to present data by treatment groups and by symptomatic/asymptomatic subjects. Secondary analyses can also be performed in subjects who report positively to events on the Supplementary PRO tools (e.g. fatigue, headache) versus those who do not. These comparisons will not rely on device removal.

- Serum or plasma nickel and titanium levels in subjects with Essure and adjudicated hypersensitivity reactions can be compared to serum or plasma nickel and titanium levels in subjects with Essure without hypersensitivity reactions as well as to serum or plasma nickel and titanium levels in laparoscopic tubal ligation subjects (with and without adjudicated hypersensitivity reactions). Secondary analyses can also be performed in subjects who report positively to events on the Supplementary PRO tools (e.g. fatigue, headache) versus those who do not. These comparisons will not rely on device removal.
- NiLPT and chromium LPT results (both the continuous measurement as well as the positive / negative assessment) in subjects with Essure and adjudicated hypersensitivity reactions can be compared to NiLPT and chromium LPT results in subjects with Essure without hypersensitivity reactions as well as to NiLPT and chromium LPT results in laparoscopic tubal ligation subjects (with and without adjudicated hypersensitivity reactions). Secondary analyses can also be performed in subjects who report positively to events on the Supplementary PRO tools (e.g. fatigue, headache) versus those who do not. These comparisons will not rely on device removal.
- An individual subject's serum or plasma nickel and titanium levels and NiLPT can be compared to baseline levels in order to assess any change. In addition, in cases of removal, subsequent post-removal levels can also be compared.

Autoimmune diseases

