14.3 Adjudication Committee

Section modified by Amendment 2 (Modification 27).

An adjudication committee for allergy / hypersensitivity and immunology / autoimmune events will be formed. This will consist of a group of experts in allergy / immunology who are also experienced in evaluating immunological symptoms in subjects with medical devices. A gynecologist will be included. For possible hypersensitivity/allergic reactions, the committee will develop a list of Medical Dictionary for Regulatory Activities (MedDRA) terms that could represent hypersensitivity or allergy, irrespective of treatment group or investigator's assessment of relatedness. This list will be provided to investigators and will be stored in the ISF. All events with these terms will be sent to the committee for adjudication. In addition to the list of MedDRA terms, all subjects who are evaluated for pelvic pain will also be reviewed by the adjudication committee to assess whether or not an element of hypersensitivity could have played a role in the subject's pain. In the event that a subject reports that an AE is an allergic reaction, the AE will be investigated by the adjudication committee, regardless of whether the AE term is on the pre-established list.

For each case, the committee will receive:

- information from the eCRFs (blinded as to group assignment);
- baseline and supplemental study laboratory values;
- medical records (e.g. medical history or relevant medical information), consultant reports, other diagnostic studies (e.g. laboratory, radiological), and operative reports, as applicable, as well as any pathology reports.

In addition, all cases with a suspected or confirmed diagnosis of an autoimmune disease will be evaluated by the committee. The records listed above will be provided to the committee. In cases of suspected or confirmed autoimmune diseases, the adjudication committee may also request that previously collected baseline and/or one-year frozen serum be used to run additional tests. Results of HLA type will also be provided to the committee.

The committee will operate based on the allergy / immunology adjudication committee charter.

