Additional Endpoints	
 
New exposure to metals including new cosmetic or medical permanent implants and/or piercings and its material, wear eyeglasses
 
Change from baseline to 1 Year in serum or plasma nickel level, titanium level— both categorical and continuous forms, association with adjudicated hypersensitivity/allergic/autoimmune events
 
Change from baseline to 1 Year in serum or plasma nickel level, titanium level association with adjudicated hypersensitivity/allergic/autoimmune events
 
Proportion of women who crossed over to alternate sterilization method (e.g., Essure subjects who attempted laparoscopic tubal sterilization)
 

Essure Insert Placement Procedure a	Type of hysteroscopy procedure, reason for second attempt, facility where procedure was performed, premedication, pregnancy test performed within 24 hours of this procedure, hormonal manipulation to promote atrophic or proliferate endometrium, anesthesia used, type of anesthesia used, placement technique, hysteroscopy possible, retroverted uterus, distention medium used, type of distention medium, duration of procedure, Essure procedure attempted, reason Essure procedure not attempted, experienced

	Endpoint/Variable
	AE during hysteroscopy, placement status (by tube), ostium in the field of vision during placement (by tube), if successful - number of Essure trailing coils, number of inserts used (by tube), device type, reasons for unsuccessful placement (by tube), primary reason for unsuccessful placement (by tube), first line confirmation test to be performed, investigator's rating of ease of use of the Essure device, physician's rating of procedure difficulty, experienced AE during Essure implant procedure, Primary method of contraception used just prior to procedure, Primary method of contraception used until reliance assessment, additional procedures performed in conjunction with the Essure procedure
Transvaginal Ultrasound a	Reason for TVU, facility where TVU performed, uterine position at time of TVU, insert detected (by tube), implant location (by tube), reason for unsatisfactory placement (by tube), TVU results satisfactory to allow the subject to rely on Essure, individual who performed TVU, individual who interpreted TVU, physician's rating of procedure difficulty, experienced AE during TVU

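### The adjudication committee sees the study markers before it decides, so descriptive marker comparisons by adjudicated status are open to incorporation bias of unknown size

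*Protocol*

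**What the plan says.** **What the committee receives.** For hypersensitivity events, Protocol 5.2.1 states: "Information forwarded to the adjudication committee will include all laboratory work for the subject, including baseline, 12 month (if applicable), and unscheduled draws". The autoimmune paragraph of the same section repeats the rule: "Information forwarded to the adjudication committee will include all laboratory work for the subject". Protocol 9.6.1.1 lists the nickel LPT (NiLPT), chromium LPT, nickel, titanium and an inflammatory cytokine panel as the evaluation, and says that the results "will be forwarded to the sponsor directly by the central lab and will be made available to the adjudication committee". Protocol 14.3 puts "baseline and supplemental study laboratory values" in the dossier for every case. For suspected or confirmed autoimmune disease it adds: "Results of HLA type will also be provided to the committee". For hypersensitivity cases, HLA is covered only by the general wording on laboratory work.

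**Who decides.** "The final determination of whether or not a hypersensitivity / allergic event has occurred will be made by this committee" (Protocol 5.2.1). The autoimmune paragraph says the same of autoimmune disorders, and SAP 6.4 confirms both.

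**What is compared afterwards.** Protocol 9.6.1.1 describes comparisons by adjudicated status, for example: "Serum or plasma nickel and titanium levels in subjects with Essure and adjudicated hypersensitivity reactions can be compared to" levels in women without such reactions. Parallel items cover cytokines and HLA, and the two proliferation tests, for both hypersensitivity and autoimmune disorders. SAP Table 2 lists change from baseline to 1 year in nickel and titanium, with "association with adjudicated hypersensitivity/allergic/autoimmune events". It names no other marker for that association.

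**What does not use adjudication.** The last part of Protocol 5.2.1 says that Supplemental PRO results will be used to form comparison groups for the laboratory work. Protocol 9.6.1.1 repeats this split as an optional secondary analysis and also plans cytokine category summaries by symptomatic status.

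**The concern.** A study objective is to find characteristics related to allergic, hypersensitivity or autoimmune-like reactions. Under Amendment 2 the sponsor judged that pathology and metallurgy would not suffice for this and added the blood-marker strategy. The markers therefore carry much of that objective.

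If the committee gives any weight to a positive NiLPT or a raised nickel level, marker-positive women are more likely to be called cases. If it discounts symptoms when the marker is negative, genuine marker-negative reactions drop out of the case group. Both push towards an apparent association, and neither shrinks as numbers grow.

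No passage in either document asks for a determination made without the marker results. The only blinding described for the committee is to treatment group. By contrast, Protocol 9.6.1.6 keeps the pathologists blind to symptoms, which protects the histology comparison in the way that the blood markers lack.

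**Working it through.** The documents give no event count, marker prevalence or acceptance rate, so there is no plan figure to reproduce. The check has two parts.

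**1. Do the documents break the loop anywhere?**
- SAP 6.2 tabulates the original assessment against the adjudicated one, but uses neither in a marker comparison.
- SAP 6.8 (sensitivity analyses) only lifts the censoring.
- SAP 6.6.2 and 6.7 regroup by analysis set and subgroup, not by any unadjudicated case definition.
- The PRO split in Protocol 5.2.1 and 9.6.1.1 and the symptomatic split in 9.6.1.1 avoid the verdict, but the SAP does not take up either of them as a marker analysis.

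**2. How large could the bias be?** Assume that a binary marker has no relation to the true reaction or to referral. Let q1 and q0 be the probabilities that the committee accepts a referred case when the marker is positive and negative, and let r be the share of women referred. All three are assumptions. Write odds(p) = p/(1 − p).
- Among referred women: spurious OR = odds(q1) / odds(q0).
- Whole cohort, with non-referred women counted as non-cases: spurious OR = odds(r·q1) / odds(r·q0).

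| q1 vs q0 | Among referred | Cohort, r = 10% | Cohort, r = 30% |
|---|---|---|---|
| 50% vs 25% | (0.50/0.50)/(0.25/0.75) = 3.00 | (0.05/0.95)/(0.025/0.975) = 2.05 | (0.15/0.85)/(0.075/0.925) = 2.18 |
| 40% vs 30% | (0.40/0.60)/(0.30/0.70) = 1.56 | (0.04/0.96)/(0.03/0.97) = 1.35 | (0.12/0.88)/(0.09/0.91) = 1.38 |
| 25% vs 20% | (0.25/0.75)/(0.20/0.80) = 1.33 | (0.025/0.975)/(0.02/0.98) = 1.26 | (0.075/0.925)/(0.06/0.94) = 1.27 |
| q1 = q0 | 1.00 | 1.00 | 1.00 |

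The cohort columns are closer to the contrast in Protocol 9.6.1.1 for NiLPT, nickel, titanium and cytokines, because these are measured in all women at baseline and 12 months (Protocol 9.2.1, 9.2.2.7 and 9.6.3.1). They do not fit chromium LPT, which Protocol 9.6.3.1 draws only in women with symptoms. For chromium LPT the referred column is the nearer guide.

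The last row shows that a decision made without sight of the markers removes the spurious association, whatever the acceptance rate or referral share.

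**The case against.** The strongest reply has four parts.

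- **Expert committees properly use laboratory evidence.** This stands. For autoimmune disease, serology is part of diagnosis, and nothing here argues against a final determination made with the results in view.
- **Seeing a result is not the same as using it as a criterion.** This also stands in part. The weighing and ordering of evidence belongs to the charter, which might already stage it. The documents therefore show exposure to bias, not its size.
- **The comparisons are exploratory and descriptive.** Protocol 9.6.1.1 mostly says they are possible, SAP 4.2 rules out confirmatory tests, and SAP 6.4 keeps comparative analysis to the main endpoints. This lowers the stakes, but a descriptive estimate is biased in the same way as a tested one.
- **Unaffected groupings are already planned.** This is correct and limits the point to comparisons split by adjudicated status.

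A reader might infer that the plan formally tests every marker against a case definition built from it, so that the whole marker programme is circular and uninterpretable. The documents do not support that. There is no formal marker test, the SAP association covers nickel and titanium only, no passage makes a marker a criterion for case status, and the PRO and symptom groupings stand apart from the verdict. Nor should the 3.0 be read as the distortion in the comparison with all women without a reaction, since it applies among referred women only.

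**Conclusion.** The point holds for one set of analyses: marker comparisons and associations by adjudicated hypersensitivity, allergic or autoimmune status. They are open to incorporation bias because the committee holds the markers when it decides, and no planned analysis removes that influence.

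The size cannot be known from the documents. Under no true relation, the assumed acceptance gaps of 50% vs 25% and 40% vs 30% give spurious odds ratios of 3.0 and 1.56 among referred women. Cohort-wide, at an assumed 10% to 30% referral, they give about 2.05 to 2.18 and 1.35 to 1.38. A charter that already withholds the markers at first reading would bring these to 1.00.

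The main endpoints are not affected. This is a worthwhile, inexpensive improvement to secondary descriptive analyses. The autoimmune part will add little, since Protocol 9.6.1.1 expects very few such cases.

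**What to change.** **1. SAP (Table 2 and the marker analyses), with matching text in Protocol 9.6.1.1.**
- Make the symptom or Supplemental PRO grouping from Protocol 5.2.1 the lead analysis for nickel, titanium, NiLPT, chromium LPT, cytokines and HLA, and define how symptomatic status is assigned.
- Add a comparison by referral to the committee, whatever its verdict, through any route in Protocol 14.3: the MedDRA list, evaluation for pelvic pain, an adverse event that the subject reports as allergic, or suspected or confirmed autoimmune disease.
- Keep the association with adjudicated status as secondary, labelled as subject to incorporation bias.
- State that chromium LPT will have few comparators in any grouping, because women without symptoms are not tested.

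**2. Charter and adjudication form, for cases not yet adjudicated.** The committee records a determination with the study marker results withheld, then opens them and records the final determination. Show marker comparisons by the first determination separately, and do not pool them with cases adjudicated earlier. The final determination remains the main endpoint.

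**Cost.** Slightly more committee time per case, one extra recorded decision and some extra tables, with no new samples or visits. The referral grouping treats every referred woman as a case and so dilutes any true association. Step 2 reaches only cases still to come. The protocol version is dated 28 JUN 2022 and US distribution of the device was to stop after 31 DEC 2018, so those may be few. That is why step 1 should carry most of the weight.

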5.2.2 Physician and subject characterizations

- Characteristics of physicians performing the procedures;
- Characteristics of subjects undergoing Essure Confirmation Test compared to subjects who do not comply with the requirement for Essure confirmation testing.

